10.4.1 Adverse Events

For analyses purposes, adverse events will be classified as pre-treatment emergent, treatment emergent, or post-treatment emergent. Adverse events which start (or increase in severity) during the period from the signing of informed consent up to, but not including, the first dose of study drug will be considered pre-treatment emergent. Adverse events which start (or increase in severity) during the period from the first dose of study drug through completion of the final Follow-up Visit (Day 57) will be considered treatment emergent. Adverse events which start (or increase in severity) after the completion of the Follow-Up Visit will be considered post-treatment emergent. For AEs with partial start dates, missing month will be imputed with January and missing day will be imputed with 1.

Adverse event summary tables will be presented for AEs only and will include the following:

- All treatment-emergent adverse events (TEAEs) or by severity or by relationship,
- Related (defined as possibly related or related) TEAEs,
- TEAEs leading to treatment discontinuation,
- Serious TEAEs, and
- Frequently reported TEAEs.

Summaries will be presented by Medical Dictionary for Regulatory Activities (MedDRA) system organ class and preferred term using frequency counts and percentages (i.e., number and percentage of patients with an event as well as total number of events). Patients with multiple occurrences of the same adverse event or a continuing adverse event will be counted once; only the maximum severity level of this AE will be presented in the severity summaries; and only the worst/highest relationship level of this AE will be presented in the relationship summaries. A separate table will summarize all TEAEs when each of them is considered unique, hereafter referred as adverse event count table. In addition, a listing containing individual patient adverse event data for all deaths and other serious and significant adverse events will be provided, separately. All adverse events including pre- and post-treatment adverse events will be presented in individual patient data listings.

Narratives of deaths, serious and significant adverse events, including early withdrawals due to adverse events, will also be provided.

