5.2 Dosage Schedule

5.2.1 Dosing of SelK2

For those randomized to receive SelK2, patients will receive a single dose of 7.5 mg/kg SelK2 via IV administration at least 12 hours prior to but not longer than 24 hours prior to the start of the TKA surgery. SelK2 will be given as an approximately 100 mL IV infusion over approximately 30 minutes (\pm 15 minutes).

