5.2.2 Dosing of Enoxaparin

For those randomized to receive enoxaparin, patients will receive 40 mg enoxaparin administered via SC injection 12 hours after TKA surgery followed by daily SC injections of 40 mg enoxaparin through and including Day 11 (\pm 2 days). Daily dosing of enoxaparin should continue until the venogram is completed. At the discretion of the PI, sites also have the option of giving an additional 40 mg enoxaparin SC dose 12 hours PRIOR to TKA surgery.

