7.1 Procedures for Handling and Reporting Adverse Events

7.1.1 Adverse Event

An **adverse event** (AE) is any undesirable medical event affecting a patient during a clinical trial. An AE can therefore be defined as any sign, symptom, syndrome, or new illness that appears while a patient is participating in this clinical study (from Randomization to final study visit (either Day 57 Visit or Early Discontinuation Visit)) or, if present at baseline, worsens in a patient during the period of observation in the clinical study and that may impair the well-being of the patient. The term also covers laboratory findings or results of other diagnostic procedures that are considered to be medically important (e.g., that require unscheduled diagnostic procedures, treatment measures, or result in withdrawal from the study). An AE may or may not have a causal relationship with the study drug. The period of observation for AEs is defined as from the point at which the patient is randomized into the study to the completion of the Follow-Up Phase assessments at Day 57 (or the Early Discontinuation Visit, if patient early discontinues).

An AE may be:

- A new illness;
- Worsening of a sign or symptom of the condition under treatment or of a concomitant illness;
- An effect of the study drug;
- Unrelated to participation in the clinical study; or
- A combination of one or more of these factors.

Surgical procedures themselves are not AEs; they are therapeutic measures for conditions that require surgery. However, the condition for which the surgery is required may be an AE. Planned surgical measures permitted by the study protocol and the condition(s) leading to these measures are not AEs.

Each AE is to be recorded only once on the “Adverse Event” eCRF page with *seriousness* and maximum *intensity* that occurred over the duration of the event. Each event also should be evaluated with respect to *causality* and *actions taken*. All AEs are to be monitored and recorded from the point of study Randomization through Day 57 (or earlier if patient discontinues from the study). For all AEs that require the patient to be discontinued from the study, the event(s) will be followed until final resolution or stabilization of the event(s). Note that unexpected SAEs should be reported as outlined in Section 7.1.2. Adverse events may be identified by spontaneous patient report or from standardized open-ended verbal probes.

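### Treatment-emergent AE tables start at first dose, so on a clock-time reading they cover surgery and the next 12 hours for SelK2 patients but not for enoxaparin patients without the optional pre-operative dose

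*Combined protocol and SAP*

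**What the plan says.** Section 10.4.1 counts as treatment-emergent "Adverse events which start (or increase in severity) during the period from the first dose of study drug through completion of the final Follow-up Visit". Events arising "up to, but not including, the first dose of study drug will be considered pre-treatment emergent". All the summary tables named there are of treatment-emergent events: overall, by severity or relationship, related, leading to discontinuation, serious and frequent. The event-count table is no exception: "A separate table will summarize all TEAEs when each of them is considered unique". Events outside the window are covered by this sentence: "All adverse events including pre- and post-treatment adverse events will be presented in individual patient data listings". Deaths and serious or significant events also get a separate listing and narratives.

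The first dose falls at different points by arm. SelK2 is given "at least 12 hours prior to but not longer than 24 hours prior to the start of the TKA surgery" (Section 5.2.1), and Section 5.2.3 has the same timing for the combination arm. In the enoxaparin arm, "patients will receive 40 mg enoxaparin administered via SC injection 12 hours after TKA surgery" (Section 5.2.2), and at the PI's discretion "sites also have the option of giving an additional 40 mg enoxaparin SC dose 12 hours PRIOR to TKA surgery".

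Three other sections bear on the start point. Section 3.4.2 treats enoxaparin as study drug and starts the Treatment Phase at surgery for enoxaparin patients dosed only afterwards. Sections 6.5.2.1 and 7.1.1 collect AEs from randomisation in all arms. Section 10.4 bases safety analysis on data from randomisation to Day 57, but its AE summaries are still of treatment-emergent events and refer to Section 10.4.1.

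**The concern.** A first-dose window is a drug-exposure definition and is fair between arms when first doses fall at about the same point in each patient's course. Here they can fall on opposite sides of an operation, and the operation itself generates AEs. The hours left out for part of the enoxaparin arm are the intra-operative and first post-operative hours.

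Overall safety and tolerability is a primary objective (Section 2.0), and the incidence of treatment-emergent AEs is one of the endpoints named for it in Section 10.4. If the windows differ, the by-arm tables mix drug effect with window length. The tendency is against SelK2, so the artefact would not conceal a SelK2 excess. It would make a real early excess hard to tell from a definitional one using these tables alone. The comparison of combination against enoxaparin has the same problem, because SelK2 opens the combination window before surgery.

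**Working it through.** The documents state no figure for this point, so there is none to reproduce. The check is a timeline, followed by the conditions that change its result.

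**Timeline.** Let D be the duration of surgery (not given; assumed 1 to 3 h). Pre-operative and post-operative intervals are from Sections 5.2.1 to 5.2.3.

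| Patient | Window opens | Window time from start of surgery to 12 h after it |
|---|---|---|
| SelK2, alone or in combination | 12 to 24 h before surgery | D + 12 h = 13 to 15 h |
| Enoxaparin, optional dose given | 12 h before surgery | D + 12 h = 13 to 15 h |
| Enoxaparin, no optional dose | 12 h after surgery | 0 h |

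- Gap between SelK2 and enoxaparin not pre-dosed: (12 to 24) + D + 12 = 24 to 36 h plus D. Of this, D + 12 h is peri-operative.
- Gap between SelK2 and pre-dosed enoxaparin: (12 to 24) − 12 = 0 to 12 h, all before surgery.

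**What moves the size.** Let r be the risk of a given preferred term starting in the peri-operative gap, equal in all arms and not recurring; f the share of enoxaparin patients pre-dosed; and w the share of gap events that worsen after first dose and so re-enter the tables. None of these is in the documents. With n patients per arm:

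- SelK2 tabulated = n × r
- Enoxaparin tabulated = n × r × [f + (1 − f) × w]
- Artificial difference = n × r × (1 − f) × (1 − w)

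To show how the formula behaves (not as an estimate), take n = 95, the planned arm size in Section 10.1, and r = 10%, so that SelK2 shows 95 × 0.10 = 9.5 patients.

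| f | w | Enoxaparin patients tabulated | Difference |
|---|---|---|---|
| 0 | 0 | 0 | 9.5 |
| 0.5 | 0 | 95 × 0.10 × 0.5 = 4.75 | 4.75 |
| 0.5 | 0.5 | 95 × 0.10 × 0.75 = 7.125 | 2.375 |
| 1 | any | 9.5 | 0 |

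The result scales in proportion to r. In the row for any treatment-emergent AE the difference is smaller, because a patient with a later event of any kind is counted anyway. If the adaptive arm opens, the SelK2-only arm closes early, so proportions carry over but the counts out of 95 do not.

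**Date or time.** The wording of the pre-treatment rule suggests clock time, but Section 10.4.1 does not say so and refers to AE start dates only. Section 10.3.2.3 has a same-day rule for medications; there is no equivalent for AEs. If AEs were classified by date with same-day events counted, and enoxaparin started on Day 2 as scheduled in Table 1, Day 2 events would be tabulated in all arms. If surgery ended after noon, a dose 12 h later would fall on Day 3 and Day 2 events would drop out again for patients not pre-dosed.

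**Start points side by side.** Section 3.4.2 uses dosing, or surgery for enoxaparin given only afterwards. Section 10.4 uses randomisation for the data set. Section 10.4.1 uses first dose. Section 10.4.1 does not take up the surgery anchor, and Section 10.4 does not lift the treatment-emergent restriction. The three need reconciling.

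**The case against.** The strongest counter-case is about certainty and consequence. Nothing is lost from the database: AEs are collected from randomisation, listed in full, and narrated when serious or significant. The table list in Section 10.4.1 is not stated to be exhaustive. The primary safety outcome is adjudicated bleeding, tabulated separately without a treatment-emergent restriction, and VTE is counted from randomisation (Section 10.3.3). Safety analysis is descriptive, so no test or decision rule depends on these tables, and the Steering and Safety Committee's AE incidence in Section 10.5 carries no stated restriction to treatment-emergent events. All of this stands and limits the weight of the point. It does not supply a by-arm summary with equal windows.

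The clause on increased severity also brings some enoxaparin events back. That stands, but how many is unclear. Section 7.1.1 says "Each AE is to be recorded only once on the" AE page, with its maximum intensity, and the protocol does not say that the date of worsening is recorded. Section 6.5.2.1 refers to separate eCRF completion guidelines, which may settle this, so it is missing detail and not a demonstrated fault.

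A reader might go further and infer that SelK2 must show more treatment-emergent AEs whenever any enoxaparin patient is not pre-dosed. The documents do not support that: classification by date can remove the difference for Day 2 events, worsening can restore events, and later AEs dilute the any-event row. A reader might also infer that the bias can be put as a range of percentage points. It cannot, because every input to such a range would be assumed.

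**Conclusion.** The point holds as a defect of the treatment-emergent AE tables, and it should be corrected. Taken by clock time, Section 10.4.1 gives SelK2 patients 13 to 15 peri-operative hours of observation (for an assumed operation of 1 to 3 h) that enoxaparin patients without the optional dose do not get. With equal true risk, the tables would tend to favour enoxaparin. The conclusion rests on the clock-time reading, on enoxaparin counting as study drug (as in Section 3.4.2), and on some enoxaparin patients not being pre-dosed. The size is unknown and may be nil. The point does not extend to adjudicated bleeding or VTE, and it does not suggest that harm from SelK2 would be hidden.

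**What to change.** In Section 10.4.1, present the by-arm AE and SAE tables from one landmark common to all arms: randomisation, from which AEs are already collected, or the start of surgery as a peri-operative anchor. These can replace the first-dose tables or stand beside them. Report the share of enoxaparin patients given the pre-operative dose, so that any retained first-dose table can be interpreted. Reconcile the start points in Sections 3.4.2, 10.4 and 10.4.1. If first-dose tables are kept, state whether AEs are classified by date or by time, and how a date of worsening is obtained.

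The cost is a short wording change, handled under Section 12.5 because this is protocol text, and one extra table or set of tables. Tables from randomisation need no new data, and the definitional difference between arms disappears. The downside is that some events before dosing enter the comparison. No dosing or clinical procedure changes.

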6.2 Screening Phase

This screening process will be conducted to confirm the patient's eligibility to participate in this study based on a review of all inclusion and exclusion criteria. The following procedures are to be performed within 30 days prior to Day 1 of the Treatment Phase (note, medical history can be used to confirm criteria as long as data was collected/verified within the 30-day screening phase):

1. Signed the Informed Consent;
2. Demographics including age, gender, race;
3. Medical history;
4. Complete physical examination (refer to section 6.5.2.3);
5. 12-lead ECG;
6. Vital signs including sitting blood pressure, pulse rate, respiratory rate, and temperature after sitting for 3-5 minutes, and body weight;
7. Collection of clinical laboratory samples (blood and urine) to be shipped to the central lab for evaluation of hematology, blood chemistry, coagulation parameters and urinalysis (See Section 6.5.2.2 for complete listing of analyses);
8. HIV antibody testing, Hepatitis B and C testing;
9. High Sensitivity C-reactive Protein (hsCRP) and D-dimer sample collection;
10. In female patients of child bearing potential perform serum pregnancy test; and
11. Record concomitant medications and transfusions.

Patients who meet all of the inclusion criteria and none of the exclusion criteria during the Screening Phase will be eligible for the study. At the Investigator's discretion, patients that are excluded from the study may be rescreened for study inclusion at a later date that is at least two weeks following the initial study exclusion. The primary reason for patient exclusions will be recorded in a screening log for patients who are not randomized.

No study-specific procedures will be performed prior to completion of informed consent by patient.

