10.4 Safety Analysis

All treatment-emergent AEs and SAEs will be summarized by treatment using the MedDRA coding system, by system organ class, preferred term, relationship to Study Drug and severity (See Section 10.4.1).

Incidence of bleeding events (as adjudicated by the CIAC) including the following will be tabulated by treatment:

- 1) Major Bleeding event (MB),
- 2) Clinically Relevant Non-Major Bleeding event (CRNMB),
- 3) Minor Bleeding event, or
- 4) Combination of MB and CRNMB

Additionally, the overall safety profile of study drug will be assessed in terms of the following safety and tolerability endpoints:

- Incidence of treatment-emergent adverse events (TEAEs),
- Clinical laboratory values (hematology, serum chemistries, urinalysis, and coagulation parameters),
- ECGs,
- Vital signs.

These safety endpoint measures will be tabulated by treatment arm and study visit (and timepoint, where appropriate) and may also be presented as change and percent change from baseline, as appropriate.

Safety analysis will be based on the set of data associated with the period from randomization through the final Follow-Up Phase visit (Day 57). All Safety analyses will be performed on the safety population. Descriptive analysis of the above safety parameters will be performed.

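### The imputation rule for partial AE start dates has no floor at first dose, so some post-dose AEs are dated before dosing and leave the TEAE summary tables

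*Combined protocol and SAP*

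**What the plan says.** Section 10.4.1 classes each AE by when it starts or worsens. From consent "up to, but not including, the first dose of study drug will be considered pre-treatment emergent"; "from the first dose of study drug through completion of the final Follow-up Visit (Day 57) will be considered treatment emergent"; anything later is post-treatment emergent. For incomplete dates the section says: "For AEs with partial start dates, missing month will be imputed with January and missing day will be imputed with 1". It makes no exception for a partial date that could lie on or after the first dose.

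The AE summary tables rest on the treatment-emergent class. The list opens with "All treatment-emergent adverse events (TEAEs) or by severity or by relationship" and goes on to related, discontinuation, serious and frequent TEAEs. Events in the other classes appear only in listings: "All adverse events including pre- and post-treatment adverse events will be presented in individual patient data listings".

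Three other places bear on the point:

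- Section 7.1.1 sets the collection window: "All AEs are to be monitored and recorded from the point of study Randomization through Day 57".
- Section 6.2 fixes how far consent can precede dosing: "The following procedures are to be performed within 30 days prior to Day 1 of the Treatment Phase".
- Section 10.4 handles bleeding separately: "Incidence of bleeding events (as adjudicated by the CIAC) including the following will be tabulated by treatment".

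**The concern.** The rule always picks the earliest date that the known parts allow. Randomization is on Day 1 and first dose follows within a day or two, so almost every recorded AE is post-dose. An imputed date before randomization contradicts the plan's own collection window, and also the randomization-to-Day-57 period that Section 10.4 sets for the safety analysis.

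The error runs one way: it removes events from the TEAE tables and never adds them. For a given partial date it is most likely when onset is close to dosing and surgery. Overall safety and tolerability is a primary objective (Section 2.0), and TEAE incidence is a named safety measure (Section 10.4).

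Section 10.3.2.3 uses the same January/1st convention for medications. There it does little harm, because a drug started before dosing and continued afterwards still counts as concomitant. AEs have no matching protection. The severity-increase clause will rarely help, since Section 7.1.1 has each AE entered once, at its maximum intensity.

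**Working it through.** The plan states no figure here, so there is none to reproduce. The check applies the rule literally.

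**Inputs from the plan.** Missing day becomes 1; missing month becomes January (10.4.1). AEs run from Day 1 to Day 57 (7.1.1), so onset is t = 0 to 56 days after a Day 1 dose. Consent precedes Day 1 by up to 30 days (6.2).

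**Assumptions, not in the plan.** Dose dates are uniform over a 365-day year, onsets are uniform within the window, and dates are compared by calendar day.

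**Example (illustrative dates).** First dose 17 June 2019, true onset 20 June 2019.
- Day missing: imputed 1 June, before the dose.
- Day and month missing: imputed 1 January, before the dose.

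The rule gives the right class in other cases. With onset 5 July and the day missing, the imputed date is 1 July. With dose 17 December 2019, onset 5 January 2020 and only the year known, it is 1 January 2020. With the dose on 1 June and the day missing, the imputed date equals the dose date.

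**Formula, day missing, 30-day month.** The imputed date precedes the dose when onset falls in the dose month and the dose was not on the 1st. At lag t that share is (29 − t)/30 for t ≤ 28, and zero beyond.
- t = 0 to 10, mean t = 5: (29 − 5)/30 = 0.80.
- t = 0 to 56: the sum of (29 − t) over t = 0 to 28 is 435; 435/30 = 14.5; 14.5/57 = 0.25.

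**Formula, day and month missing.** Onset must fall in the dose year, with the dose not on 1 January: (364 − t)/365.
- t = 0 to 10: 359/365 = 0.984.
- t = 0 to 56, mean t = 28: 336/365 = 0.921.

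**Full enumeration with real month lengths** (every 2019 dose date crossed with every lag), giving the share of truly post-dose AEs dated before the dose:

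| Onset after dose | Day missing | Day and month missing |
|---|---|---|
| 0-3 days | 91.8% | 99.3% |
| 0-10 days | 80.3% | 98.4% |
| 11-56 days | 12.8% | 90.5% |
| 0-56 days | 25.8% | 92.1% |

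**Which class they fall into.** The pre-treatment class starts at consent, so a date imputed to before consent fits no class. Among misplaced events over 0-56 days, the share before consent depends on the gap from consent to dose:

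| Consent before dose | Day missing | Day and month missing |
|---|---|---|
| 1 day | 93% | 99.7% |
| 14 days | 28% | 96% |
| 30 days | 0% | 91% |

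Either way the event is not a TEAE.

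**After the fix below,** the imputed date cannot precede the dose when the known parts allow a later onset, so the share of post-dose AEs misplaced is 0% by construction.

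**The case against.** The best defence is that the affected set is small. A date must be partial, and its known part must match the dose month or year. Patients stay at least two nights after surgery (Section 3.4.2) and AEs are assessed throughout Days 1 to 11, so a missing day is least likely just where the error rate is highest. Later contacts, on Days 21, 29, 43 and 57, are at most 14 days apart before visit windows, so an unknown month should be rare. SAEs are due within 24 hours (7.1.2), potential endpoint events preferably so (7.2), and Section 9.2 promises edit checks for missing data. All of this stands. It limits the likely count but does not make the rule right: the plan provides for partial dates, and no other section corrects how it dates them.

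A reader might also infer more than the documents support:

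- **That the primary safety outcome is undercounted.** It is not directly affected. Bleeding is tabulated from central adjudication, which does not depend on TEAE status.
- **That events vanish from the report.** They leave the summary tables only. All AEs are listed, and deaths and serious or significant AEs also have a separate listing and narratives (10.4.1).
- **That open-label treatment makes the loss unequal between arms.** The AE assessment schedule is the same for all arms (Table 1), and nothing shows that partial dates differ by arm.

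**Conclusion.** The point holds in this limited form. Followed as written, Section 10.4.1 dates some post-dose AEs before first dose and removes them from every listed TEAE summary table. It affects day-missing AEs with onset in the dose month, unless dosing was on the 1st, and month-missing AEs with onset in the dose year, unless dosing was on 1 January. Partial dates outside those conditions are classed correctly.

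The 80% figure belongs to the first 10 days only; across the whole collection period the day-missing figure is about 26%. All the percentages are shares of partial-date AEs and rest on uniform dose dates and onsets. Because the documents do not say how many partial dates to expect, the number of TEAEs lost cannot be estimated. No efficacy conclusion depends on the rule. It should still be corrected, because it is a stated rule that gives a wrong result in a known direction.

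**What to change.** Replace the imputation sentence in Section 10.4.1 with a rule to this effect:

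- When the known parts of the start date, and any stop date, are compatible with onset on or after first dose, impute the later of the current rule's date and the first-dose date.
- Otherwise keep the current rule. When only a later year is known, the result remains 1 January of that year.
- Treat an AE as treatment-emergent unless the known date parts or the stop date show that it began before first dose. This also settles the class of an AE whose start date is wholly missing, which the present text does not cover.

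The cost is a short text change and one programming rule, with no new data; it should be in place before database lock. The downside is that a few partial-date AEs arising between randomization and first dose would count as TEAEs. That gap is about a day or two. It is longest for enoxaparin patients first dosed after surgery, where it includes the operation. The rule then errs towards counting an event, which is the conservative direction for safety.
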